3.4 Safety variables

Safety endpoints during the treatment period are:

- Incidence of treatment-emergent adverse events (TEAEs; see section 4.2.5.1) and hypoglycemic events (see section 4.2.5.2) over the treatment period
- Antibodies to exenatide, physical examination (height), laboratory measurements (clinical chemistry, hematology and urinalysis including calcitonin and CEA concentrations), vital signs (blood pressure and heart rate) and ECGs (overall assessment) from screening Visit 1 (Week -3) or baseline Visit 3 (Week 0) to Visit 11 (Week 28), and to each intermediate visit as applicable
- Tanner pubertal stage at baseline Visit 3 (Week 0), Visit 5 (Week 4), Visit 7 (Week 12), Visit 9 (Week 20) and Visit 11 (Week 28)

Safety endpoints during the follow-up period are:

- Adverse events of special interest
- CEA and calcitonin concentrations
- Prescription medications
- Body weight, height and Tanner pubertal stage

3.5 Exploratory safety variables

The exploratory safety endpoint is change in estimated glomerular filtration rate (eGFR) from baseline Visit 3 (Week 0) to Visit 11 (Week 28).

3.6 Definition of study variables

Refer to Section 4.3 for details on conventions such as visit windowing and handling of duplicate assessments.

3.6.1 Study baseline

The baseline measurement is defined as the last non-missing (either numerical or character) value, including values from unscheduled visits, collected on or prior to the first dose of study medication in the double-blind treatment period on/at Visit 3 (Week 0). Assessments carried out on the date of the first dose are assumed to have been done pre-dose unless time information indicates otherwise.

The baseline measurement for demographic and baseline characteristic data in patients who do not get treated is defined as the last non-missing value collected on or prior to Visit 3 (Week 0).

If the last non-missing value ties with another non-missing value happening at the same day and time (or same day, if time is not collected) then the mean of the values will be used.

If the baseline value is missing for a given variable, change from baseline will be missing.

Baseline for BMI will be calculated from last non-missing values for height and weight, even if they were at separate dates.

3.6.2 End of study treatment measurement

For completers, end of study treatment measurement is the last non-missing post-baseline measurement obtained at or prior to Visit 11 (Week 28).

If patient discontinues prior to Week 28 (Visit 11), then the end of study treatment measurement is the last non-missing post-baseline measurement obtained at or prior to ED visit.

If patient discontinues prior to Week 28 (Visit 11) and there is no ED visit, then the end of study treatment measurement is the last dose date +1 (or + 30 days if discontinued due to SAEs and other clinically significant or related AEs).

3.6.3 Change and percent change from baseline

Change from baseline to any post-baseline Week t is defined as follows:

$$C_{Week\ t} = M_{Week\ t} - M_{baseline},$$

Where:

- $C_{Week\ t}$ is the change from baseline at Week t,
- $M_{Week\ t}$ is the measurement at Week t,
- $M_{baseline}$ is the baseline measurement.

Percent change from baseline to any post-baseline Week t is defined as follows:

$$P_{Week\ t} = 100 \times (M_{Week\ t} - M_{baseline}) / M_{baseline}.$$

If the baseline value is zero, the percent change will be missing.

3.6.4 Rescue therapy

Rescue therapy is defined as any new antidiabetic concomitant medication or changes to background oral-diabetic medication, for exacerbation of diabetes.

Treatment with insulin may be given for emergency reasons during the treatment period. If the period of insulin use exceeds 10 days during a 3-month period, then a decision to discontinue study treatment will be made after consultation between the investigator and the Sponsor's clinical research physician.

Background oral antidiabetic medication (metformin and SU) were to be continued throughout the study at the same dose and schedule as before study entry. However, metformin dosage could be adjusted for up to 10 consecutive days or 10 days in a 30-day period and the SU dosage could be decreased in response to hypoglycemia.

Changes in background metformin and SU will be programmatically derived from the concomitant therapy (CCT) oral anti-diabetic medication (OAM) CRFs and reviewed by the clinical team prior to unblinding. Increases identified as potential rescue episodes will be queried at the site-level to determine whether rescue therapy or not.

New antidiabetic medication will be programmatically identified from the CCT OAM CRFs where the Anatomical Therapeutic Chemical (ATC) code begins with "A10".

A rescue episode will be defined as the first unique rescue therapy entry on the CCT OAM CRFs as derived as above. If a patient has multiple entries, the first will be considered the point at which the patient was rescued.

For patients who require initiation of rescue therapy and continue study treatment, only data before initiation of rescue therapy will be included in the primary efficacy analysis. If HbA1c is measured before rescue therapy, then we will include the HbA1c measurement. If HbA1c is measured on the date of first rescue therapy but no time information is available, then HbA1c will be included in the primary efficacy analysis. Sensitivity analyses including data after initiation of rescue therapy will be carried out to test the robustness of the missing data assumption.

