### 8.7. Concomitant Therapy

Patients will not be allowed to take any of the listed excluded medications during the treatment period ([Section 7.2](#), Exclusion Criteria).

For oral medications that are dependent on threshold concentrations for efficacy, such as antibiotics, patients should be advised to take those drugs at least 1 hour before study drug injection. If such drugs are to be administered with food, patients should be advised to take them with a meal or snack when study drug is not administered. Concomitant medications should not be taken or administered on the morning of prescheduled clinic visits.

It may be possible that due to an emergency, some patients will require treatment with insulin. If the period exceeds 10 days during a 3-month period, then the decision to keep the patient in the study should be made after consultation between the investigator and the Sponsor's clinical research physician. Each situation will be considered separately, in order to differentiate between real clinical needs and non-compliance. The decision will be documented by a note to the investigator's file.

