ED	Early discontinuation
eGFR	Estimated glomerular filtration rate
FAS	Full analysis set
FSG	Fasting serum glucose
FSI	Fasting serum insulin
GCV	Geometric coefficient of variation
GSD	Geometric standard deviation
HbA1c	Glycated hemoglobin A1c
HOMA-B	Homeostasis model assessments – beta-cell functions

Abbreviation or special term	Explanation
HOMA-S	Homeostasis model assessments – insulin sensitivity
ICH	International Conference on Harmonisation
ITT	Intent-to-Treat
LLN	Lower limit of normal range
LMP	Lifestyle modification program
MAR	Missing at random
MedDRA	Medical Dictionary for Regulatory Activities
MI	Multiple imputation
MMRM	Mixed model repeated measures
MNAR	Missing not at random
OAM	Oral anti-diabetic medication
OC	Observed case
PBO	Placebo
PD	Protocol deviations
PK	Pharmacokinetic
PT	Preferred term
QD	Once daily
QW	Once weekly
RD	Registered dietitian
SAP	Statistical Analysis Plan
SD	Standard deviation
SI	Standard International (Unit)
SMBG	Self-monitored blood glucose
SOC	System organ class
SU	Sulfonylurea
TEAE	Treatment emergent adverse events
ULN	Upper limit of normal range
WHODD	World Health Organization Drug Dictionary

AMENDMENT HISTORY

Date	Brief description of change
22th April 2020	
Due to change of company for the analysis of this study from Amylin Pharmaceuticals, LLC to IQVIA, the Statistical Analysis Plan has been fully rewritten from Version 1.0. Rewritten to be consistent with Study D5551C00002 where appropriate. Summaries and analysis of long-term safety follow-up period included. Due to power considerations, efficacy analysis comparisons will be between both exenatide treatment arms combined versus placebo.

	
Updated to allow for possibility of analysis of treatment period data and safety follow-up period data separately

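### SAP 3.6.4 defines rescue as any new antidiabetic drug but derives it only from forms named for oral medication, so insulin recorded elsewhere would not be flagged

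*SAP*

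**What the plan says.** SAP 3.6.4 sets the definition: "Rescue therapy is defined as any new antidiabetic concomitant medication or changes to background oral-diabetic medication, for exacerbation of diabetes". It has no limit by route of administration, but it does require an indication. The next paragraph of that section adds: "Treatment with insulin may be given for emergency reasons during the treatment period". Protocol 8.7 agrees: "It may be possible that due to an emergency, some patients will require treatment with insulin". Under both documents, insulin for more than 10 days in a 3-month period leads to a consultation about whether the patient continues, not to automatic withdrawal.

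The derivation follows. Changes in background metformin and sulfonylurea are "derived from the concomitant therapy (CCT) oral anti-diabetic medication (OAM) CRFs and reviewed by the clinical team prior to unblinding", and increases that look like rescue are queried with the site. For drugs that are not background therapy, "New antidiabetic medication will be programmatically identified from the CCT OAM CRFs", using ATC codes that begin with A10. The rescue episode is then the first rescue entry on those same forms. The SAP abbreviation list gives OAM as "Oral anti-diabetic medication".

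The flag has wide use. SAP 3.6.4 and 4.2.4.2 remove HbA1c after rescue from the primary MMRM. Section 4.1.4 extends the exclusion to all efficacy endpoints. Table 3 in 4.2.4.1 gives the primary estimand a hypothetical strategy with data after the event excluded. Section 4.2.1.4 summarizes and lists rescue therapy.

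**The concern.** The definition and the rule that implements it differ in scope. The definition covers every antidiabetic drug, while the rule searches forms whose name covers oral drugs only. Insulin is an injectable that both documents expressly allow in a patient who stays on study, and a form named for oral drugs is an uncertain place to find it. The A10 filter would recognize insulin, but a filter finds only what is in the dataset it is applied to.

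A missed episode would leave insulin-lowered HbA1c in the primary analysis as if it reflected randomized treatment alone. It would do the same in the pattern-mixture sensitivity analysis of the primary estimand. In the HbA1c-goal analysis, where a patient with no usable Week 28 value counts as a non-responder, a patient on insulin could count as a responder. Rescue would also be undercounted in its own table.

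**Working it through.** **Step 1: what each rule covers.**

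| Item | Scope in the documents |
|---|---|
| Definition of rescue (SAP 3.6.4) | Any new antidiabetic drug, or a change to background oral therapy, for exacerbation of diabetes |
| Insulin on study (SAP 3.6.4, Protocol 8.7) | Allowed in an emergency |
| Source for new drugs (SAP 3.6.4) | CCT OAM CRFs, ATC code A10 |
| Source for the rescue date (SAP 3.6.4) | First rescue entry on the CCT OAM CRFs |
| Clinical review and site query (SAP 3.6.4) | Background metformin and sulfonylurea changes |
| Physician review before lock (SAP 4.2.1.4) | Prohibited medications; the named list omits insulin |

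Neither review is written to pick up new insulin, and no other data source is named.

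**Step 2: which patients are exposed to the gap.** Confirmed loss of glycemic control leads to discontinuation (Protocol 6.1.7 and 7.4). Metformin or sulfonylurea added or altered beyond the 10-day limits does so too (Protocol 7.4). HbA1c after discontinuation of study drug is excluded from the primary analysis whatever the rescue flag says (SAP 4.2.4.2). The gap therefore concerns patients who receive insulin or another new injectable and continue study drug.

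**Step 3: the plan's own power.** SAP 1.3 gives 122 randomized 2:1, a difference of 0.6, an SD of 1.0 and about 87% power; SAP 4.1.2 gives a two-sided 5% level. With 81 and 41 patients:

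- standard error = √(1/81 + 1/41) = 0.192
- noncentrality = 0.6 / 0.192 = 3.13, with 120 degrees of freedom
- power = 87.4% by noncentral t (87.8% by the normal approximation), which reproduces the stated figure.

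**Step 4: how unflagged insulin would act.** Let fp and fe be the shares of placebo and exenatide patients with unflagged insulin, and g the amount by which it lowers Week 28 HbA1c. The difference becomes 0.6 − (fp − fe) × g. The documents give none of these three quantities, so the values below are assumptions that show only the mechanism.

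| fp − fe | g = 0.5 | g = 1.0 | g = 1.5 |
|---|---|---|---|
| 0 points | 0.600 (87.4%) | 0.600 (87.4%) | 0.600 (87.4%) |
| 5 points | 0.575 (84.5%) | 0.550 (81.2%) | 0.525 (77.6%) |
| 10 points | 0.550 (81.2%) | 0.500 (73.5%) | 0.450 (64.4%) |
| 15 points | 0.525 (77.6%) | 0.450 (64.4%) | 0.375 (49.2%) |

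Each cell shows the difference and, in brackets, the power. With equal use in the two groups there is no shift. If use were commoner on exenatide, the sign would reverse. The table does not measure what the fix would recover, because excluding the flagged values also costs information. Nor does the 87% starting point allow for discontinuation.

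**The case against.** The strongest objection is that the CRFs are not in the documents. The plural CRFs and the separate abbreviation for concomitant therapy also fit a reading in which both the general and the oral forms are searched. A filter on the whole A10 group suggests a scope wider than oral background drugs. This stands, and it makes the consequence conditional. The visit schedule does not settle it: Protocol Attachment 1 lists concomitant medications separately from oral antidiabetic dose, but the latter is a diary item for the day before the visit.

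Second, the definition requires use for exacerbation of diabetes, whereas the insulin allowance speaks of an emergency. Not all emergency insulin need be rescue, and the SAP does not say that it is. This also stands, and it means that an A10 code alone should not create a rescue episode.

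Third, the reach is limited. Data after discontinuation of study drug are excluded anyway. Short insulin courses would probably move Week 28 HbA1c by less than the larger effects in the table. The supplementary estimand keeps data after rescue, so it does not depend on the flag. All medications are listed, so insulin use would be visible. These points reduce the likely effect but do not repair the primary analysis: the supplementary analysis answers a different question, and a listing does not change which values enter the MMRM.

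A reader might go further and infer that insulin is certainly missed, that post-insulin HbA1c certainly stays in, or that the trial loses a known amount of power. The documents support none of these: they do not show where insulin was recorded, how often it was used or what it did to HbA1c.

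**Conclusion.** The point holds in conditional form. As written, the derivation is narrower than the definition and the estimand that it serves, and neither planned review closes the gap. If insulin or another injectable was recorded outside the OAM forms, and the patient continued study drug, later HbA1c enters the primary MMRM against the stated exclusion rule. The likely direction is toward no effect, on the assumption that such use is commoner on placebo. The size cannot be determined from the documents. The power figures above are illustrations on assumed inputs, not estimates. Because two programmers could build different primary datasets from the same text, this is worth correcting and is more than a missing detail.

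**What to change.** Amend SAP 3.6.4 before unblinding, as follows:

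- Apply the ATC A10 search to all concomitant-therapy records, oral anti-diabetic and general, and name the forms.
- Send new A10 entries, including insulin, through the same blinded clinical review and site query already used for background increases, to confirm that the drug was given for exacerbation of diabetes.
- Take the earliest confirmed entry on any form as the rescue date.
- Use the same source for the rescue summary and listing in SAP 4.2.1.4.

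This changes only how the analysis data are derived; no treatment rule is touched. The cost is one more input dataset and a few more blinded queries. If the OAM forms already hold insulin, the rescue dates stay as they are.

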### **8.5.2. Sulfonylurea**

The concomitant SU will be continued throughout the study at the same dose and schedule as before study entry. The SU dosage may be decreased in response to hypoglycemia.

If the patient is receiving a fixed-dose combination of metformin and an SU, the SU dosage may be decreased in response to hypoglycemia; however, the metformin dosage should remain unchanged. If a fixed-dose combination is available that would permit reduction of an SU dosage (as described above) without a change in metformin dosage, a fixed-dose combination pill can be used. If a fixed-dose combination does not meet these criteria, the metformin and SU should be administered as separate pills.

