4.1.4 Handling of data post rescue medication

Instances of patients receiving rescue medication is defined in Section 3.6.4.

Efficacy

For all efficacy endpoints data collected after the first administration of rescue therapy will be excluded from the descriptive statistical summary and inferential statistical analyses.

However, data collected after initiation of rescue medication will be included in several sensitivity and supportive analyses for the primary analysis to provide a comprehensive view of the treatment effect (see more details in Section 4.2.4.3).

Safety

Because patients can continuously receive study medication concurrent with the rescue therapy, all safety data (except eGFR) collected during the rescue medication use will be summarized together with data collected prior to the rescue therapy. The exploratory analysis of eGFR will be repeated twice (once including data after rescue therapy and once excluding data after rescue therapy).

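### SAP 3.6.4 defines rescue by its reason, but new antidiabetic drugs are identified only by an A10 code on the oral-medication forms, with no stated check of reason

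*SAP*

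**What the plan says.** SAP 3.6.4 opens with a definition that carries a reason: "Rescue therapy is defined as any new antidiabetic concomitant medication or changes to background oral-diabetic medication, for exacerbation of diabetes". It then gives two derivation routes.

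- **Background metformin and SU.** Changes are derived from the CCT OAM "CRFs and reviewed by the clinical team prior to unblinding". For dose increases there is a further step: "Increases identified as potential rescue episodes will be queried at the site-level to determine whether rescue therapy or not".
- **New drugs.** "New antidiabetic medication will be programmatically identified from the CCT OAM CRFs where the Anatomical Therapeutic Chemical (ATC) code begins with" A10. The section states no review, query, reason or duration criterion for this route.

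Both routes feed one date: "A rescue episode will be defined as the first unique rescue therapy entry on the CCT OAM CRFs as derived as above". SAP 4.1.4 gives the consequence: "For all efficacy endpoints data collected after the first administration of rescue therapy will be excluded from the descriptive statistical summary and inferential statistical analyses". The same section makes an exception for sensitivity and supportive analyses of the primary endpoint.

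The protocol allows two situations that can produce an A10 record without loss of glycemic control. Under Protocol 8.5.2, a patient on a fixed-dose metformin and SU product may need the SU lowered after hypoglycemia: "If a fixed-dose combination does not meet these criteria, the metformin and SU should be administered as separate pills". Protocol 8.7 foresees insulin: "It may be possible that due to an emergency, some patients will require treatment with insulin". SAP 3.6.4 repeats the insulin allowance. It requires consultation only when use passes 10 days in 3 months, and it does not say how shorter use is classed.

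**The concern.** The derivation for new drugs does not carry out the section's own definition. Whether treatment was started for exacerbation is a clinical question that an ATC code cannot answer. The SAP recognizes this for background changes and provides a blinded review, but it states no such step for new entries.

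Two kinds of error become possible. A permitted entry not made for exacerbation may be taken as rescue. Alternatively, because the search is described only for the oral anti-diabetic medication forms, insulin started for exacerbation may not be found.

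The primary estimand in SAP Table 3 excludes data after rescue, so the flag decides which HbA1c values enter the primary MMRM. For the HbA1c goals, a patient without a usable Week 28 value counts as a failure. In the pattern-mixture sensitivity analysis (SAP 4.2.4.3), removed exenatide values are imputed on the placebo trajectory.

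**Working it through.** **1. Definition against derivation (SAP 3.6.4)**

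| | Background metformin/SU change | New antidiabetic drug |
|---|---|---|
| Found by | Program, CCT OAM forms | Program, CCT OAM forms, A10 code |
| Clinical review before unblinding | Stated | Not stated |
| Site query | Stated for increases | Not stated |
| Reason (exacerbation) applied | Through review and query | No stated step |

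**2. Which entries could be affected**

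- *Fixed-dose split.* Separate metformin and SU pills would start after randomization, possibly under codes different from the combination product. The SAP does not say whether such records are new drugs or background changes. If background, they are reviewed; if new, no review is stated. Protocol 8.8 exempts SU changes made for hypoglycemia from its discontinuation rule, so such a patient can remain on study. Protocol 7.4 lists the rule without that exemption, and the two sections need to be reconciled.
- *Emergency insulin.* If the CCT OAM forms record insulin, a short course not given for exacerbation is flagged on its first day. If they hold only oral agents, insulin given for exacerbation is missed. The forms are not in the documents, so only one of these errors can apply and it is not known which.

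**3. What a false flag removes**

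HbA1c is scheduled at Weeks 4, 12, 20 and 28 after baseline, so a flag removes between one and four of four planned values. Later data for the other efficacy endpoints leave their main analyses too. SAP Table 3 lists treatment-policy analyses that keep post-rescue HbA1c for the primary endpoint. It lists none for the secondary efficacy endpoints, and the sensitivity analysis of the HbA1c goals also excludes post-event data.

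**4. Responder endpoints, per patient**

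Input: 122 randomized, 2:1 (SAP 1.3). Total EBID = 122 × 2/3 = 81.3; placebo = 122/3 = 40.7. Assume all are in the Evaluable set. One falsely flagged patient who in fact met the goal lowers the response rate by:

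- Total EBID: 100/81.33 = 1.2 percentage points
- Placebo: 100/40.67 = 2.5 percentage points

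**5. Power**

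First, the plan's own figure. Inputs from SAP 1.3: difference 0.6, SD 1.0, two-sided 5%.

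Power = Φ(0.6/SE − 1.96), with SE = √(1/81.33 + 1/40.67) = 0.192. This gives Φ(3.124 − 1.96) = Φ(1.164) = 87.8%, in line with the stated 87%. SAP 1.3 also mentions an effect of 0.455. That gives 65.9%, so 0.6 is used here.

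The documents give no rate of false flags. The shares below are assumptions:

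| Share losing Week 28 | Both arms | Exenatide only | Both arms, on top of 23% dropout |
|---|---|---|---|
| 0% | 87.8% | 87.8% | 78.3% |
| 2% | 87.1% | 87.6% | 77.5% |
| 5% | 86.1% | 87.2% | 76.2% |
| 10% | 84.2% | 86.6% | 73.9% |

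The losses are upper bounds for each assumed share, because the MMRM keeps visits before the flag.

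**The case against.** The strongest reply is that the A10 search is only an identification step. The reason condition stands in the governing definition, and a sensible programmer would apply it. A fixed-dose split involves the patient's own background drugs and may well go through the reviewed route. Emergency insulin given for worsening glycemia is true rescue, and excluding later data is then intended. SAP 4.1 requires blinded, documented decisions on the evaluability of each patient's data, and SAP 4.2.1.4 provides a listing of rescue medication and a physician review of ATC codes. The supplementary MMRM and its imputation analysis retain post-rescue HbA1c.

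Much of this is fair. A reader might infer that every new A10 entry is certain to be counted as rescue, or that all later efficacy data are lost to every analysis. The documents support neither. The definition keeps its qualifier, the route for a fixed-dose split is unstated rather than wrong, and the primary endpoint has treatment-policy analyses.

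A reader might also infer a bias of known direction, because Protocol 4.1 says exenatide raises hypoglycemia risk in SU users. An imbalance in false flags is plausible, but the documents give neither the number of fixed-dose users nor how far such patients' HbA1c would differ from the rest of their arm. The insulin error could run either way. Any figure for bias in the treatment difference would rest on invented inputs.

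What remains is that no cited safeguard adjudicates rescue for new entries. The SAP 4.1 step does not mention rescue, and the ATC review in SAP 4.2.1.4 is for prohibited medication.

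**Conclusion.** The point holds as a mismatch between definition and derivation. As written, SAP 3.6.4 applies the exacerbation condition to background changes through review and leaves it unapplied for new A10 entries. It also limits the search to forms that may or may not record insulin. Misclassification is therefore a risk, not an established fact.

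The consequence of each false flag is definite: later values leave the main efficacy analyses, and an otherwise successful patient becomes a non-responder. How many patients are affected cannot be known from the documents. The effect on power is probably small: under 2 points if 5% of both arms were affected, with no other dropout. The case for changing the text is correct classification and fidelity to the primary estimand, and it is worth doing before unblinding. It rests on the assumption that no unpublished programming specification already supplies the missing step.

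**What to change.** Amend SAP 3.6.4, for data classification only:

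- (a) Put every new A10 entry through the same clinical review before unblinding and the same site query that the section provides for background changes. Count it as rescue only if it was started for exacerbation of diabetes, and record the reason.
- (b) State that re-entry of an agent taken at baseline, under another formulation or ATC code, is a background change and not a new drug.
- (c) Search all concomitant-medication pages for A10 codes, not only the CCT OAM forms, and state where insulin is recorded.

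None of this alters what treatment a patient may receive. The cost is SAP wording and a documented, blinded judgement on what should be a short listing. The work must be finished before unblinding, since later decisions on rescue status would be open to challenge.
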